#### Imaging, vital signs, electrocardiograms, laboratory tests, and physical examination

- 16. Have a screening MRI that shows evidence of significant abnormality suggesting another potential etiology for progressive dementia or a clinically significant finding that may impact the participant's ability to safely participate in the study.
- 17. Have any contraindications for MRI, including claustrophobia or the presence of contraindicated metal (ferromagnetic) implants or a cardiac pacemaker.

18. At Visit 1, have a centrally read MRI demonstrating the presence of

- o ARIA-E
- >4 cerebral microhemorrhages
- >1 area of cortical superficial siderosis
- o any macrohemorrhage, or
- o severe white matter disease.
- 19. Have a contraindication to the PET procedure or sensitivity to the amyloid PET tracer.
- 20. Have present or planned exposure to ionizing radiation that, in combination with the planned administration of study PET ligands, would result in a cumulative exposure that exceeds local recommended exposure limits.
- 21. Have laboratory values, in relation to the reference range, of

ALT ≥2.5X ULN

AST >2.5X ULN

ALP  $\geq$ 2.0X ULN, or

TBL >1.5X ULN, except for participants diagnosed with Gilbert's syndrome.

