# 8.2.7.1. MRI Sequence Details for the Study

The standard sequences will be used to determine participant eligibility, care and safety.

The exploratory sequences will be used for exploratory analyses only and will not be used for participant management.

This table provides MRI sequences and their timing throughout the study.

Sequences	Study Visits						
	Screening/Before	Visit 4	Visit 8	Visit 12	Visit 19	ED	UV
	first infusion a	Week 4	Week	Week	Week		
			12	24	52		
Standard							
2D FLAIR	X	X	X	X	X	X	X
2D T2	X	X	X	X	X	X	X
GRE	X	X	X	X	X	X	X
DWI	X	X	X	X	X	X	X
3D T1	X	X	X	X	X	X	X
Exploratory							
3D FLAIR	X	X	X	X	X	X	X
3D T2	X	X	X	X	X	X	X
$DTI^b$	X	X	X	X	X	X	X
SWI b	X	X	X	X	X	X	X
Task-Fmri b	X						

Abbreviations: DTI = diffusion tensor imaging; DWI = diffusion-weighted imaging; ED = early discontinuation visit; FLAIR = fluid-attenuated inversion recovery; Fmri = functional magnetic resonance imaging; GRE = gradient echo; SWI = susceptibility weighted imaging; UV = unscheduled visit.

Note: standard sequences denoted by bold text and shaded cells.

<sup>a Performed either with screening MRI or another time prior to first infusion at Visit 2.

<sup>b Perform when or where available.

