- 2) The model will include all baseline exploratory MRI endpoints discussed before. The following markers will also be considered for inclusion to the model: white matter disease burden from 3D FLAIR, number of microhemorrhages at baseline form SWI, cortical superficial siderosis from SWI, PVS in centrum semi ovale, whole cortex MD, whole cortex FW, hippocampal MD and FW, whole white matter FA, fMRI peak activation in occipital cortex, hippocampal volume, cortical volume, ventricle volume, whole brain volume, cortical thickness, and CAA.
- 3) Exploratory MRI endpoints listed above will be added individually to the baseline ARIA-E risk model described in 1.
- 4) The model will include all baseline risk factors described in 1) and all exploratory endpoints described in 2).

AIC (Akaike information criteria) as well as BIC (Bayesian information criteria) statistics will be generated for each proposed model above. While both the AIC and BIC will be generated, the BIC will be used to evaluate the model. In the case of SWI endpoints, the counts of microhemorrhages and superficial siderosis will come from baseline SWI instead of its standard safety MRI equivalent. In the case of 3D FLAIR, white matter burden score will come from 3D FLAIR instead of the standard safety sequence MRI equivalent. An ROC curve (receiver operating characteristic curve) can be plotted from individual ARIA-E risk prediction model and AUC (area under the curve) will be computed to tell how each model is capable of distinguishing between ARIA-E subjects and ARIA-E free subjects. A possible AUC value is between 0.5 and 1, and the larger the AUC, the better the discriminatory ability.

Comparison between standard and exploratory MRI sequences

To assess the agreement of exploratory versus standard MRI sequences at baseline, a contingency table assessing agreement on white matter disease burden, number of microhemorrhages, and presence of cortical superficial siderosis will be evaluated separately using a Bowker's test of symmetry.

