For scans with both SWI and T2*-GRE data, Spearman's rank correlations between the number of microhemorrhages identified by SWI and that identified by T2*-GRE will be provided for baseline scans and all scans. For scans with both 3D FLAIR and 2D FLAIR data in which ARIA-E was detected in either 3D FLAIR or 2D FLAIR, a Spearman's rank correlation will be computed from the severity of ARIA-E assessed by 3D FLAIR versus that assessed by 2D FLAIR (severity will be assigned to zero if there is no presence of ARIA-E).

To assess the agreement of exploratory versus standard MRI sequences in monitoring ARIA, a contingency table assessing agreement on maximum severity, will be constructed for ARIA-E and ARIA-H separately using a Bowker's test of symmetry.

To compare temporal dynamics between exploratory versus standard MRI sequences, mean and standard deviation of number of days to 1st ARIA event will be reported for 2D FLAIR versus 3D FLAIR (ARIA-E) and for GRE (gradient recalled echo) versus SWI (ARIA-H). Percentage of exploratory scans still showing ARIA-E or ARIA-H when standard scan said ARIA-E or ARIA-H was resolved.

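### SAP 4.5.1 aims to assess agreement between exploratory and standard MRI but names only a test of symmetry, and its FLAIR severity correlation drops scans negative on both sequences

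*SAP*

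**What the plan says.** The comparison of sequences is in SAP Section 4.5.1, with the four regimens pooled. It has three parts that matter here.

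- **Baseline agreement.** The plan calls for "a contingency table assessing agreement on white matter disease burden, number of microhemorrhages, and presence of cortical superficial siderosis", and each table "will be evaluated separately using a Bowker's test of symmetry".
- **Agreement in monitoring ARIA.** The plan calls for "a contingency table assessing agreement on maximum severity, will be constructed for ARIA-E and ARIA-H separately using a Bowker's test of symmetry".
- **Rank correlations.** For ARIA-E severity on 3D versus 2D FLAIR, the Spearman correlation covers scans selected as follows: "For scans with both 3D FLAIR and 2D FLAIR data in which ARIA-E was detected in either 3D FLAIR or 2D FLAIR". Within that set, "severity will be assigned to zero if there is no presence of ARIA-E". The SWI versus T2*-GRE correlation of microhemorrhage counts has no such restriction; it "will be provided for baseline scans and all scans".

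The section also plans a descriptive comparison of days to first ARIA event, and the percentage of exploratory scans still showing ARIA once the standard scan has resolved. It names no kappa, percent agreement, sensitivity or specificity, and sets no threshold for adequate agreement. SAP Section 4.1 puts all frequentist tests at a two-sided 0.05 level.

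On eligibility, Protocol Section 8.2.7.1 says: "The standard sequences will be used to determine participant eligibility, care and safety". Protocol Section 5.2, criterion 18, excludes people whose centrally read MRI shows ">4 cerebral microhemorrhages" or severe white matter disease, among other findings.

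**The concern.** Two statistics do not match the question asked of them.

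First, Bowker's test asks whether disagreements in one direction are as frequent as those in the other. It ignores the diagonal of the table, where agreement lies. A non-significant result does not show that the sequences agree, and a significant one does not show that they agree poorly.

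Second, limiting the FLAIR correlation to scans positive on at least one sequence removes every agreed negative and keeps every scan seen on one sequence only, scored 0 on the other. Those one-sided scans pull the correlation down, so a single figure combines whether both sequences detect ARIA-E with whether they grade it alike.

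At stake is what the report can say about 3D FLAIR and SWI as substitutes for the standard sequences. It could describe agreement as good from a non-significant Bowker test, or as poor from a low FLAIR correlation, and be wrong each time.

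**Working it through.** The documents give no expected value, sample size or threshold for this comparison, so there is no stated figure to reproduce.

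**Inputs from the documents.** The scan set, the zero coding and the named tests come from SAP 4.5.1, and the 0.05 level from SAP 4.1. For scale only, SAP Section 5 gives 720 participants completing Visit 12 and ARIA-E rates of 18.5% and 11.1%, so the pooled rate is (18.5 + 3 × 11.1)/4 = 12.95%.

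**Assumed inputs.** Table counts, severity mix, scan prevalence, detection probability and reader noise.

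**1. Bowker's test.** Chi-square = sum over i<j of (n_ij − n_ji)²/(n_ij + n_ji), with k(k−1)/2 degrees of freedom.

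- Total disagreement, cells 0/50/50/0: (50 − 50)²/100 = 0, p = 1.0, kappa −1.
- Independent readings with equal margins (kappa 0), 5,000 simulated tables each: rejected in 4.8% with four equal levels and n = 400, and in 2.3% with margins 0.87/0.05/0.06/0.02 and n = 720. About 95% to 98% are therefore non-significant.
- Near-perfect agreement, cells 694/6/0/90: agreement 784/790 = 99.2%, kappa 0.96. Chi-square = (6 − 0)²/6 = 6 on 1 df, p = 0.014 (exact 2 × 0.5^6 = 0.031).
- A four-level table of 2,874 scans with 12 + 4 + 2 = 18 discordances, all one way: kappa 0.94, chi-square 18 on 6 df, p = 0.006.

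**2. Restricted correlation, presence or absence only.** Let b be the scans positive on both and d the scans positive on one only, equal in each direction. With n = b + 2d and p = (b + d)/n:

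rho = (b/n − p²)/(p(1 − p)) = −d/(b + d)

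This can never be positive. With b = 150 and d = 20, rho = −20/170 = −0.12. Adding an assumed 2,700 scans negative on both gives exact agreement 2,850/2,890 = 98.6% and kappa 0.875. For d from 5 to 40 with b of 100 or 150, kappa runs from 0.97 down to 0.70, and the restricted rho from −0.03 to −0.29.

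**3. Four severity levels, mostly moderate** (2,879 scans, 179 positive on either). Exact agreement is 98.1%, kappa 0.82 and weighted kappa 0.86. Spearman is 0.87 on all scans and 0.39 on the restricted set.

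**4. Simulated detection model.** ARIA-E in 8% of scans, severity agreeing 90% of the time when seen, misses independent between sequences. With detection probability s, the one-sided share of positive scans is 1 − s²/(1 − (1 − s)²).

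| s | One-sided share | Spearman, all scans | Spearman, restricted |
|---|---|---|---|
| 95% | 1 − 0.9025/0.9975 = 10% | 0.95 | 0.67 |
| 85% | 1 − 0.7225/0.9775 = 26% | 0.84 | 0.38 to 0.42 |
| 70% | 1 − 0.49/0.91 = 46% | 0.68 | 0.05 to 0.07 |

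The ranges come from repeat runs of the model, in which the severity mix was assumed. Weighted kappa at 85% detection is 0.82. Among scans positive on both, Spearman stays at 0.84 in all three rows. If 80% of detection outcomes are shared between sequences, the restricted figure at 85% detection rises to 0.79.

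**5. Simulated reader noise** (2,880 scans, 6% positive).

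| Noise SD | Restricted | All scans | Weighted kappa |
|---|---|---|---|
| 0.20 | 0.96 | 0.95 | 0.98 |
| 0.35 | 0.79 | 0.93 | 0.95 |
| 0.50 | 0.62 | 0.91 | 0.91 |

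**6. Baseline tables.** Eligibility is read from the standard sequences, so at baseline the standard reading is cut at 4 microhemorrhages and below severe white matter disease, while the exploratory reading is not cut. Those tables describe readings conditional on eligibility by one of the two sequences being compared.

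**The case against.** The best defence has five parts.

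- **The tables themselves are planned.** Percent agreement or kappa could be read from them, and the SAP attaches the word agreement to the tables, not to the Spearman correlation. This is true, but no such measure is prespecified.
- **There is no pass/fail rule.** A reader might infer that the plan treats a non-significant Bowker test as proof of agreement. The SAP does not say so, and testing for a systematic shift is a fair question in itself. The remaining problem is that this is the only test offered for a stated aim of agreement.
- **The correlation is not always pulled down.** A reader might infer that the restriction lowers it however well the sequences agree. The working shows otherwise: with little noise it is 0.96 against 0.95, and with mostly shared misses 0.79. Nor does the point extend to the SWI/GRE correlation, which is unrestricted.
- **A low conditional figure can be real.** At 85% independent detection, 26% of positive scans are seen on one sequence only. All-scan figures are high partly because shared negatives dominate. This stands, and is why kappa alone is not enough.
- **Consequences are small.** Sequence agreement is not a listed endpoint, and the Protocol keeps exploratory sequences out of participant management. This stands too.

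A further tempting reading is that eligibility truncation makes the baseline Bowker test reject falsely at a known rate. The documents do not support a figure: the SAP does not define the microhemorrhage categories, and under one assumed lesion model rejection ran from 1% to 24% depending on the categories chosen. Siderosis is compared as presence or absence while exclusion starts above one area, so it is not cut in the same way.

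**Conclusion.** The concern holds in limited form. Bowker's test cannot answer the stated question of agreement; this follows from its formula and rests on no assumption about the data. The either-positive FLAIR correlation combines detection and grading and can be low or negative when overall agreement is high. Its size is not determined by the documents. Under the assumed simulation inputs it runs from about 0.05 to 0.96, driven by how many detections are one-sided and whether the two sequences miss the same lesions; constructed presence/absence tables reach −0.29. The baseline microhemorrhage and white matter tables are conditional on eligibility by the standard sequences, which deserves a label but no number. The analysis is tertiary, and no primary, secondary or safety conclusion depends on it.

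**What to change.** In SAP 4.5.1:

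- Make weighted kappa with a 95% CI the agreement measure for ARIA-E severity, maximum severity, microhemorrhage category (with the categories defined) and white matter burden, and simple kappa for siderosis presence.
- Use all scans that have both sequences, including those negative on both, with a participant-level bootstrap where scans repeat within a person.
- Report positive and negative percent agreement alongside, because shared negatives dominate. In the binary example these are 300/340 = 88% and 5,400/5,440 = 99%, which shows what kappa alone would hide.
- Report the ARIA-E severity correlation separately for scans positive on both sequences. Label the either-positive version as conditional, or drop it.
- Keep Bowker's test only as a check on the direction of disagreement.
- Label the baseline microhemorrhage and white matter tables as conditional on eligibility by the standard sequences. Adding SWI from screen failures is not a dependable remedy, because Protocol 8.2.7.1 has SWI done only when or where available.

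The cost is SAP wording, a few lines of code and a little extra output. No new data are needed.

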4.6.6. Amyloid-Related Imaging Abnormalities (ARIA)

ARIA incidence was discussed in Section 4.3, Section 4.4.1, and Section 4.4.3. Severity of ARIA events was covered in Section 4.4.3.

Unless otherwise specified, safety analyses of ARIA events are based on centrally read MRI findings from both scheduled and unscheduled visits. Where applicable, ARIA-E summaries will be presented for symptomatic and asymptomatic ARIA-E. ARIA-H summaries will be presented by ARIA-H microhemorrhage and ARIA-H superficial siderosis. Macrohaemorrhage will be described separately and will not be included in the ARIA-H category.

An overview of ARIA incidence by treatment arm from safety analysis set will be presented using frequency and percentage of patients with any ARIA (ARIA-E or ARIA-H), ARIA-E, and ARIA-H as defined by safety MRIs or treatment-emergent AE clusters. The proportion of the patients with serious adverse events of ARIA, ARIA-E, and ARIA-H with or without ARIA-E will be summarized via treatment arm. The frequency and percentage of ARIA-E will be further

broken out by asymptomatic vs. symptomatic and by APOE genotype. The frequency and percentage of subjects with ARIA-H microhemorrhage, ARIA-H superficial siderosis, and macrohemorrhage will be further broken out by APOE genotype. A sensitivity analysis of overview of ARIA incidence will be performed utilizing per-protocol analysis set.

A severity shift table of ARIA-E, ARIA-H microhemorrhage, and ARIA-H superficial siderosis severity from baseline to Week 76 by visit and by treatment arm will be presented.

To investigate the onset of the first ARIA-E or ARIA-H event among different dosing regimens, Kaplan-Meier plots will be presented using safety analysis set. Besides Kaplan-Meier plots, histograms of the onset of the first ARIA-E or ARIA-H based on safety MRI may be provided to visually inspect timing of the first ARIA event across treatment arms.

From safety analysis set, mean and median duration before the resolution of ARIA-E or the mean and median duration of ongoing ARIA-E events for each dosing regimen will be derived.

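### The comparison of ARIA timing between standard and exploratory MRI uses two unpaired means with no common population, so the difference partly reflects who is included and can take either sign

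*SAP*

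**What the plan says.** The comparison is in SAP 4.5.1, in the part that sets standard against exploratory MRI sequences. Its purpose is stated: "To compare temporal dynamics between exploratory versus standard MRI sequences". The onset statistic is "mean and standard deviation of number of days to 1st ARIA event will be reported for 2D FLAIR versus 3D FLAIR (ARIA-E") and, in the same form, "for GRE (gradient recalled echo) versus SWI (ARIA-H"). The other timing output concerns offset: "Percentage of exploratory scans still showing ARIA-E or ARIA-H when standard scan said ARIA-E or ARIA-H was resolved". The four dosing regimens are pooled for all of this.

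For days to first event the SAP does not say which participants enter each mean, whether the scans must carry both sequences, or what happens to a participant positive on one sequence only. Such rules do appear in the same section for another analysis. The FLAIR severity correlation is restricted as follows: "For scans with both 3D FLAIR and 2D FLAIR data in which ARIA-E was detected in either 3D FLAIR or 2D FLAIR", and non-detection is scored: "severity will be assigned to zero if there is no presence of ARIA-E". The microhemorrhage correlation is likewise limited to scans with both SWI and GRE.

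The SAP's Kaplan-Meier plots, in 4.6.6, serve a different comparison: "To investigate the onset of the first ARIA-E or ARIA-H event among different dosing regimens, Kaplan-Meier plots will be presented".

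The table in Protocol 8.2.7.1 schedules standard and exploratory sequences at the same MRI visits. SWI carries the footnote "Perform when or where available", as do DTI and task fMRI. GRE, 2D FLAIR and 3D FLAIR do not.

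**The concern.** Days to first event is undefined for a participant who never has an event on that sequence. Without a pairing or censoring rule, the obvious way to program the table is to average over whoever is positive on 2D FLAIR, then over whoever is positive on 3D FLAIR. A case seen only on the exploratory sequence then enters one mean and not the other.

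Both sequences are acquired at the same visits, so within a participant the first-detection date can differ only by whole scan occasions. Across groups, the means can differ by weeks simply because the case mix differs. The table could therefore give the wrong sign for the question it is meant to answer.

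The ARIA-H comparison has a further problem: if SWI is missing at some sites or visits, the SWI mean rests on fewer participants than the GRE mean.

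The persistence percentage tabulates only scans where the exploratory sequence is still positive and the standard one has cleared. Two sequences with equal true persistence and some random reading disagreement would still give a percentage above zero. Without the reverse count, noise cannot be told from longer persistence.

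**Working it through.** The documents give no numerical result for this comparison, so there is no figure to reproduce. The check is whether the stated summary, on its natural reading, answers the stated question.

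**Inputs from the documents.** Post-baseline scans at Weeks 4, 12, 24 and 52 (SAP 4.4.1), that is days 28, 84, 168 and 364. For scale only: about 800 randomized and an 18.5% ARIA-E rate by Week 24 in the standard arm (SAP Section 5), giving 0.185 × 800 = 148.

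**Assumptions, not in the documents.** 148 participants are positive on the standard sequence, and the exploratory sequence detects all of them on the same day. It also finds 30 participants the standard sequence never shows. Three visit distributions are tried for the 148.

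**Formula.** With n_s shared positives at mean day m_s and n_x exploratory-only positives at mean day m_x, the gap between the two reported means is

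D = [n_x / (n_s + n_x)] × (m_x − m_s).

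The paired difference in shared positives is zero by construction, so D comes entirely from who is included. Its sign depends only on whether the extra cases fall later or earlier than the shared ones on average.

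**Worked case.** Shared positives 74/52/22/0 at the four scans: m_s = (74×28 + 52×84 + 22×168)/148 = 10,136/148 = 68.5 days. Extras 15 at Week 24 and 15 at Week 52: m_x = (168 + 364)/2 = 266. D = (30/178) × (266 − 68.5) = 33.3 days. Direct check: (10,136 + 2,520 + 5,460)/178 = 101.8 days against 68.5.

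**Range of D in days (positive means the exploratory sequence looks slower):**

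| Shared positives at Weeks 4/12/24/52 | Standard mean | 15 extra at Week 24, 15 at Week 52 | Extras 8/8/7/7 | 30 extra at Week 4 |
|---|---|---|---|---|
| 74/52/22/0 | 68.5 | +33.3 | +14.4 | −6.8 |
| 60/50/30/8 | 93.5 | +29.1 | +10.2 | −11.0 |
| 40/40/48/20 | 133.9 | +22.3 | +3.4 | −17.9 |

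**A case where the exploratory sequence really is earlier.** Take the first row and let the exploratory sequence see 10 of the Week 12 cases at Week 4: 10 × 56/148 = 3.8 days earlier on average in shared positives. Add 10 extra cases at Week 24 and 15 at Week 52. The exploratory mean is (10,136 − 560 + 1,680 + 5,460)/173 = 96.6 days, so the sequence looks 28.1 days slower. Under the other two distributions the figures are 24.5 and 18.7 days.

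**With a common denominator.** Give all 800 a time, with 364 days for those not detected. In the worked case the mean is (10,136 + 364×652)/800 = 309.3 days for standard and (18,116 + 364×622)/800 = 305.7 for exploratory. In the genuinely earlier case it is 306.2 for exploratory. The direction is then correct in both.

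**The case against.** The strongest reply is that the own-positives denominator is an inference. The SAP states no population for this table. Since it restricts both correlations in the same section to scans carrying both sequences, the sponsor may intend the same here. If the means were taken only over participants positive on both sequences, with both acquired, the problem would disappear. This stands as a caution. It does not remove the point, because the text imposes no such restriction and the summary as worded leads to the other reading.

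It is also fair that the size depends on assumed counts and that the sign is not fixed. A reader might infer that the exploratory sequences will be reported as slower. The documents do not support that: they say nothing about when exploratory-only cases would appear, and early ones push the figure the other way.

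Three other stronger readings go too far:

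- That the availability footnote undermines the FLAIR comparison, or that GRE and SWI come from different sites. The footnote does not apply to 3D FLAIR. GRE is scheduled at every MRI, so the scheduled SWI scans are at most a subset of the GRE scans.
- That the persistence percentage can only favour the exploratory sequence. A value near zero would show no added persistence. It is one-sided, not predetermined.
- That the sponsor might discard or adopt a sequence on this table. The SAP attaches no test, threshold or decision rule to it, and Protocol 8.2.7.1 keeps exploratory sequences out of participant management.

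Finally, the planned contingency tables of maximum severity may reveal cases seen on one sequence only. They do not show when those cases appeared, so they do not repair the timing comparison.

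**Conclusion.** The point holds in limited form. As written, the timing comparison has no common population or pairing rule. On its natural reading, the difference between means mixes detection timing with case mix. Under the assumed counts, a sequence that is never later looks about 22 to 33 days slower if 30 exploratory-only cases are split between Weeks 24 and 52, and about 7 to 18 days faster if they all fall at Week 4. These figures show the possible size and the indeterminate sign; they do not predict the trial's result. They rest on the inferred denominator, on 148 shared positives, and on the assumed visit distributions and 30 extra cases.

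For ARIA-H, the SWI participants may also be a subset of the GRE participants. The persistence percentage is incomplete without its reverse. The analysis is exploratory, descriptive and pooled over arms, so the primary endpoint, power and error rate are not affected. This is an improvement worth making, not a threat to the trial's main conclusions.

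**What to change.** In SAP 4.5.1, extend the both-sequences rule already used for the correlations to the timing comparison, so that only scans with both sequences count. Then, for 2D against 3D FLAIR and for GRE against SWI:

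- among participants positive on either sequence, report the numbers first seen earlier on the exploratory sequence, on the same scan, later, or on one sequence only;
- in participants positive on both, report the within-participant difference in first-detection day;
- report persistence in both directions: exploratory still positive when standard has resolved, and standard still positive when exploratory has resolved, each with its denominator.

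The data are already planned for collection. The cost is a short SAP wording change, one small table, and slightly fewer participants in the SWI comparison.
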